Assessments of primary and secondary outcome measures will occur at the time points

diagramed in Figure 5. Details regarding the specific assessment tools and measures to be used are described below and listed in **Table 2**. The primary outcome variables for Aim 1 (Spinal Cord Injury Pain Instrument (SCIPI)⁸⁰ score of ≥ 2 , and Neuropathic Pain Symptom Inventory score⁸⁹) will be collected during each scheduled assessment (full and abbreviated assessments), with additional outcome measures recorded less frequently (during full assessment sessions only: 4 times during the study).

Randomization and blinding procedures:

A blocked randomization procedure will be used, so that for each eight patients enrolled, four will be allocated to TENS and four to Sham TENS. A computer-generated random assignment sequence will only be accessible to the study staff member responsible for delivering TENS treatments. The PI of the study, the researchers evaluating pain diagnoses, and the research subject will not be informed of the treatment allocation assigned. All subjects will be told that they may or may not feel the stimulation from the TENS unit during treatment sessions due to the parameters of the study. The stimulation parameters of the TENS unit will not be visible to the subject, so that subjects will not obviously know to which study group they were randomized.

Treatment procedures:

(a) *TENS device*: The TENS 7000 Dual Channel battery-powered digital stimulator (Roscoe Medical, Ohio, USA) will be used. This device provides for adjustable frequency/pulse rate, pulse width, and amplitude, as well as recording of session data (settings and duration of treatment session). The TENS 7000 device has two channels. Each channel will be connected to two self-stick square electrodes (thus, a total of 4 electrode pads will be used) with dimensions of 2 inches by 2 inches. New electrode pads will be used for each treatment session.

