Subjects will be withdrawn from the research without their consent if the PI or other study staff, including trained clinicians, determine that the subject may experience adverse events of greater than mild severity and of greater than 10% frequency. If the TENS stimulation is not tolerated after adjustment of electrode location and/or after reduction of stimulus amplitude, then the subject will be withdrawn from the study and will receive no further treatments.

Participants who either self-withdraw from treatment or who are withdrawn by the PI or study staff from the treatment portion of the study, will continue to be followed during all time points after the treatment sessions have terminated, unless the participant does not want to participate in follow-up session for the study.

14) Risks to Subjects*

TENS therapy poses minimal risks to patients, as outlined below.

- a. Skin irritation: Persons undergoing TENS treatment may experience minor skin irritation as a result of the electrode placement.
- b. Painful or unpleasant sensory sensations: TENS may evoke painful or unpleasant sensations for a brief period of time while the appropriate intensity level is being determined.
- c. Emotional upset: Persons with disability may become upset at having questions asked about their disability and the pain conditions associated with their SCI.

Use of the TSA-II device also poses risks:

- d. Thermal pain testing can result in sensations that are unpleasant and which may lead to short-lived, mild-to-moderate anxiety and discomfort. Temporary mild redness around the area tested may occur but will be short-lasting.

To minimize the specific risks outlined above, the following procedures will be in place:

- a. Electrode skin irritation can be reduced by cleaning the skin before electrode placement. The risk of this occurring is low. Electrodes will not be placed near

open wounds. The treatment and control groups will be monitored by the research staff continually throughout each treatment session.

b. The research assistant or other research staff responsible for delivering the TENS treatments will be present during the entire 30 minute treatment session so that if discomfort occurs, the stimulus level can easily be reduced or the TENS electrodes can be removed, and summon one of the study physicians if evaluation is needed.

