Potential participants for this study will be recruited through the JMH inpatient SCI rehabilitation services. All subjects who are at least 18 years of age and who are admitted to the Jackson Rehabilitation Hospital/Lynn Rehabilitation Center with a traumatic spinal cord injury will be assessed for eligibility. Using the inclusion and exclusion criteria provided above, the inpatient SCI rehabilitation physician ([name]) will access Jackson electronic medical record information for this purpose. If the patient meets criteria, the study physician will approach the patient and ask if he/she would agree to have a study team member talk to them about the study for possible enrollment.

All those who agree will be approached in person or over the phone by a research staff member for possible enrollment within 4 months of their injury. Patients who express interest in the study will be informed in detail of the procedures and timeline of the study. The research staff member will then review the informed consent document with the participant, including potential risks and benefits of the study, and assurance that their refusal to be a part of the study, or to withdraw from the study, will not influence their clinical services at UM/JMH. Any questions the patient has will be answered by the study staff member or referred to the PI and/or study physicians for further discussion with the patient. (See section #27 for full consenting procedures.)

Cash and check payments will be made to subjects based on completion of each treatment and assessment portion of the study: 1) \$25 will be paid for each treatment session attended; 2) \$150 will be paid for each full assessment session completed (partial payment, in the amount of \$75, may be paid if the participant completes only the questionnaire portion of this visit, but does not complete the sensory assessment portion); 3) \$25 will be paid for each brief assessment session completed; and 4) a \$50 bonus will be conferred at the end of the study for subjects who complete 90% or more of study treatments, visits, and phone assessments. Up to a total of \$1075 at completion of the study is available for each subject. Cash payments will be given to the subject immediately after each treatment session and in-person assessment session. Check payments may be made via mail for phone assessment if payment in person is not feasible.

22) Local Number of Subjects

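### The staff member who delivers TENS or sham can see the full randomization sequence in advance, and the protocol neither describes concealment nor keeps that person out of consent, enrolment or scheduling

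*Combined protocol and SAP*

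**What the plan says.** Section 9 (Randomization and blinding procedures) sets 1:1 allocation in blocks of fixed size: "for each eight patients enrolled, four will be allocated to TENS and four to Sham TENS". On access to the list it says: "A computer-generated random assignment sequence will only be accessible to the study staff member responsible for delivering TENS treatments". On blinding it says: "The PI of the study, the researchers evaluating pain diagnoses, and the research subject will not be informed of the treatment allocation assigned".

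Section 14 (Risks to Subjects) identifies who treats: "The research assistant or other research staff responsible for delivering the TENS treatments will be present during the entire 30 minute treatment session". Section 18 (Setting) allows sessions in the subject's home, given by a member of the research staff.

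Section 21 (Recruitment Methods) describes entry to the trial. The inpatient physician checks eligibility in the medical record, and then "the study physician will approach the patient and ask if he/she would agree to have a study team member talk to them". Those who agree are "approached in person or over the phone by a research staff member for possible enrollment". After that, "The research staff member will then review the informed consent document with the participant".

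Section 19 (Resources Available) says that the duties of individual staff are listed in the IRB application, which is not among the documents reviewed.

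**The concern.** Blinding and allocation concealment are different safeguards. The plan addresses the first by naming who is not told a subject's arm. It does not address the second, which is that nobody who can influence entry or its timing should know the next arm before the subject is committed. Giving the treating staff member the sequence, rather than each subject's assignment as it falls due, goes further than the task requires.

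The stakes are selection and timing. A person who knows the next arm and also consents or schedules subjects could, even without intent, press more or less hard in the consent discussion, or bring baseline and the first session forward or back. In this trial timing is flexible and is linked to the primary endpoint, so such influence could reach the main comparison.

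**Working it through.** The plan gives no figure for concealment that could be reproduced. The check compares the provisions and adds one calculation on the blocks.

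**1. Access needed and access given.** Sham requires the amplitude to be turned down by hand at each session (section 9, Sham TENS parameters), so the treating person must know the arm of each subject in treatment. Nothing in that task requires the arm of a subject not yet enrolled. The text gives access to the sequence and mentions no stepwise release.

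**2. Roles and stated access.**

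| Task | Who, as stated | Access to the sequence |
|---|---|---|
| Eligibility check, first approach | Inpatient or study physician (section 21) | None stated |
| Enrolment approach, consent | An unspecified research staff member (section 21) | Not stated |
| Sensory testing | PI, or staff trained by the PI (section 14) | PI not informed; others not stated |
| Treatment | Research assistant or other research staff (sections 14 and 18) | Yes |
| Pain diagnosis | Two researchers (section 9) | Not informed |

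The labels for enrolling and treating are generic and could describe the same person. No sentence says that they do, and none says that they may not.

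**3. Route from foreknowledge to the primary endpoint.**
- Room in consent: about 175 patients are expected to be eligible and about 98 to consent (section 22). 98/175 = 56%, so 77 eligible patients do not enter.
- Room in timing: treatment may start at any point up to four months after injury, with four weeks as the target (section 9, Overview).
- Timing and baseline pain: the Overview expects a four-week start to reach about 75% of eventual cases before symptoms appear. A later start would be expected to find more subjects already in pain.
- Baseline pain and outcome: under Hypothesis 1a (section 11), a subject with early neuropathic pain counts as positive at 12 months only if the pain is rated at least 4 out of 10. Other subjects are positive on a SCIPI score of 2 or more for a pain at or below the level of injury.
- Analysis: the primary test is a two-proportion z test with no covariates, so it does not correct for an imbalance in baseline pain or start time.

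**4. What the fixed block adds.** For the list-holder it adds nothing, since every assignment is already visible. For someone without the list who knows the block size and all past assignments, an assignment is certain once one arm has used its four places. The last k assignments of a block all fall in one arm with probability 2 × C(8−k, 4)/C(8, 4). Summing over k = 1 to 4:

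2 × (35 + 15 + 5 + 1)/70 = 112/70 = 1.6 of 8 (20%).

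Since 98 = 12 × 8 + 2, and the first two places of a block are never forced, the trial total is 12 × 1.6 = 19.2, or about 19 of 98. Over all 70 orderings of a block, always guessing the under-represented arm (and guessing at random when the arms are level) is right 5.33 times in 8 (66.6%), against 50% for someone who knows no past assignments.

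**The case against.** The strongest reply is that access is deliberately narrow. One role holds the list, someone must know the arm to deliver sham, and the PI, the diagnosing researchers and the subject are not informed. All adult traumatic admissions are assessed, the physician makes the first approach with no stated access to the list, and subjects are randomized whether or not they have neuropathic pain at entry. The team includes a coordinator, a nurse and other assistants, so the roles may well be separate, and the IRB application may say so.

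Most of this stands, and it rules out some stronger readings:
- A reader might infer that assignments are open to the whole study team. The text limits access to the treating role.
- A reader might infer that the list-holder decides who is approached. Section 21 gives screening and first contact to the physician; what remains is possible influence on consent and scheduling.
- A reader might take the 20% as the measure of the problem. It does not apply to the list-holder, and it applies to others only if past assignments leak; the documents show no such leak.

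The reply does not supply a concealment mechanism. Withholding arms from the PI and the assessors is blinding, and a possible separation of duties recorded elsewhere is not a rule in this protocol. The objection that prospective changes come too late is fair if enrolment ended as planned, and the fix allows for that.

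**Conclusion.** The gap is real but limited. The protocol opens the sequence in advance to the person who treats, describes no way of concealing the next assignment, and does not bar that person from consent, enrolment or scheduling. The list-holder can foresee 98 of 98 assignments. That assumes access to the sequence means access to all of it, which is the plain reading because no staged release is described.

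Bias follows only if the list-holder also takes part in consent or scheduling, and the documents leave that open. A reader might conclude that randomization has been undone; nothing in the documents supports this. Neither the size nor the direction of any effect on the treatment difference or the type I error can be derived, because the documents do not say how baseline pain varies with start time. This is a cheap improvement, not a flaw that invalidates the trial.

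**What to change.** **For any allocation still to be made.** Have existing personnel with no role in screening, consent, treatment or assessment hold the sequence, or place it in a locked electronic module. Release each assignment to the treating staff member only after consent and baseline are complete. State in section 9 who enrols and who schedules. Use varying block sizes and keep them out of the protocol. The cost is a small administrative burden at each randomization.

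**If enrolment has closed.** It was planned to end on 1 January 2022 (section 7), and this version is dated 18 July 2022. In that case:
- Report who held the list, whether that person consented or scheduled subjects, and when each assignment was revealed.
- Tabulate baseline neuropathic pain and time from injury to treatment start by arm. Balance would be reassuring but would not prove concealment, and a modest imbalance can arise by chance.
- Add a sensitivity analysis of the primary endpoint adjusted for both variables. It would not remove selection on unmeasured factors.

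On the planned dates there was still time to specify this. A subject enrolled on 1 January 2022 was injured no earlier than about September 2021, so that subject's 12-month assessment falls in September 2022 or later, after this version. The cost is a few lines of reporting and one extra model on data already collected.

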- We will use the components of the International SCI Pain Basic Data Set, version 2.0 (ISCI PBDS2),⁷⁹ to record the presence of pain, the interference of pain on activities of daily living, mood, and sleep, locations of pains, intensity of pain, the onset of the pain condition, and whether treatments are currently being used for the pain condition. The guidelines provided in the ISCI PBDS2 regarding diagnosis of pain will be used to classify each pain condition a subject reports. For each research subject at each full assessment session (baseline, end of treatment, and 12 months post-injury), two experienced SCI pain researchers (Drs. [name] and [name]) will evaluate the characteristics of each pain a subject has to make a determination of diagnosis. These characteristics will be taken from the ISCI PBDS2 and the International SCIPEDS questions and other assessments regarding pain characteristics (e.g., location relative to LOI, quality of pain) and sensory testing results (see “Quantitative Sensory Testing” section, below). If the two assessors differ with regard to diagnosis, review of data and evaluations will be discussed by the assessors and consensus will be reached. *These pain classifications will be used to compare with NeuP classification identified by a SCIP score of ≥2, and to evaluate relationships between different pain types and other variables measured [Aims 2].*
- We will use selected components from the newly-published International SCI Pain Extended Data Set (ISCI PEDS),⁹³ to record temporal characteristics of the pain (“How long does your pain usually last?”, and “When during the day is the pain most intense?”), as well as treatments the subject is using for pain (“treatments” section of the ISCI Pain Extended Data Set). For each treatment the subject can respond with regard to whether he/she is currently using the treatment, how often, the dose, and adverse effects, and his/her global impression of change⁹⁴ *Responses to the treatment*

section will be used as a supplemental assessment of pain severity⁹² [Aim 1]. Lower doses of pain treatments suggest lower pain severity, while higher doses suggest a greater need for pain relief/ higher pain severity.

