 - Quantitative sensory testing (QST) techniques will be used as reliable and sensitive measures of STT and SC-MLS function^{74, 106, 107} in areas above, at, and below the neurological level of injury using a TSA-II device (Medoc, Ltd). Measures of vibratory, warm, and cool detection thresholds, hot and cold pain thresholds, and temporal summation of thermal pain will be recorded during full assessment sessions. *The longitudinal tracking of these measures will allow for the assessment of: 1) whether use of TENS early after injury that alters STT and/or DC-MLS function is related to the effectiveness of TENS on measures of chronic neuropathic pain at 12 months post-injury [Aim 1]; and 2) the predictability of chronic neuropathic pain based on specific somatosensory sensitivity measures (i.e., thresholds to innocuous tactile and thermal stimuli; thresholds to noxious stimuli; pain ratings for suprathreshold pain stimuli) [Aim 2].* These measures and device (TSA-II) have been previously used by our group to investigate associations between sensory function and chronic pain across cohorts of subjects with chronic SCI^{7,8, 74, , 108} and have been used in many other chronic pain populations to examine mechanisms, diagnoses, and relationship to analgesic response.¹⁰⁹⁻¹¹¹
 - A neurological examination utilizing the International Standards for Neurological Classification of Spinal Cord Injury¹¹² will be obtained from the medical record if available. The sensory/motor scores for each dermatome/myotome will be recorded, as well as the neurological level of injury and American Spinal Injury Association Impairment Scale. *These variables will be used as bedside assessments of sensory function for comparison with QST measures and for their potential predictive ability for the later development of chronic neuropathic pain [Aim 2].*

v. Emotional function:

- The Patient Health Questionnaire 9 (PHQ-9)¹¹³ will be used to assess depression symptom severity. It is a 9-item questionnaire based on the Diagnostic and Statistical Manual of Mental Disorders, 5th Edition, Revised (DSM-IVR)¹¹⁴ criteria for major depression and that has been validated across a number of patient populations,^{113, 115} including SCI.¹¹⁶

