symptoms at the 12 month post-injury time point. It is anticipated that those who show reduced sensitivity to noxious stimuli after TENS treatments will exhibit a lower risk for chronic neuropathic pain. A repeated measures regression analysis, including appropriate covariates (e.g., demographic and injury-related factors, concomitant treatments, amplitude setting of TENS treatments), will assess whether changes in evoked pain sensitivity will be a significant predictor of neuropathic pain at 12 months post-injury in the TENS treatment group.

Hypotheses 2a, 2b, and 2c:

Chi square analyses, t-tests, and correlations across all subjects (with TENS group assignment as a covariate) will be used to separately examine whether demographic variables (age and minority status), psychological characteristics (pain catastrophizing, depressive symptoms severity, and levels of resilience), and measures of evoked pain sensitivity (pain thresholds and ratings of suprathreshold noxious stimuli) measured at baseline can predict the presence and severity of chronic neuropathic pain at 12 months post-SCI. Separate sub-analyses will also be conducted with regard to the impact of these factors on pains with different diagnostic categories (nociceptive pain, neuropathic pain).

Data security / Quality control:

All research personnel will complete and maintain trainings regarding privacy and data security as required. All personnel will receive training regarding all study procedures as required for their role, as assigned and overseen by the PI, to insure data quality and integrity of the science.

Data for the study will be recorded on paper, using the most-updated and approved study forms. These paper documents will be stored in locked file cabinets in rooms 3.156 and 3.153B of the Christine E. Lynn Rehabilitation Center ([name]). This room is locked and is accessible only by those who have been given card access. These paper documents will be stored for at least 3 years after the final termination of the grant.

Data from the paper documents will be entered into a password protected electronic database that will receive periodic and thorough data quality checks through established procedures. This

electronic file will not contain any personally-identifiable information, and will be maintained for at least 3 years after the final termination of the grant.

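### The assessors may use QST results to diagnose pain type, and the Aim 2 sub-analyses by diagnostic category then test QST as a predictor of that diagnosis

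*Combined protocol and SAP*

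**What the plan says.** Section 9, assessment tools, part ii (pain intensity and symptoms): two experienced researchers diagnose every pain a subject reports "at each full assessment session (baseline, end of treatment, and 12 months post-injury"). Their inputs are the basic and extended pain data sets and "other assessments regarding pain characteristics (e.g., location relative to LOI, quality of pain) and sensory testing results", with a cross-reference to the QST section. Differences are settled by consensus. The resulting classifications are compared with SCIPI ≥ 2 and also serve "to evaluate relationships between different pain types and other variables measured" under Aim 2.

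Section 9, part iv (sensory function): one stated purpose of QST is to assess "the predictability of chronic neuropathic pain based on specific somatosensory sensitivity measures". The measures there include vibration, warm and cool detection thresholds as well as hot and cold pain thresholds.

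Section 11, Hypotheses 2a, 2b and 2c: the target is neuropathic pain one year after injury, and demographic and psychological variables are tested as its predictors. For QST, the plan asks whether "measures of evoked pain sensitivity (pain thresholds and ratings of suprathreshold noxious stimuli) measured at baseline can predict the presence and severity". A further sentence brings in diagnostic category: "Separate sub-analyses will also be conducted with regard to the impact of these factors on pains with different diagnostic categories".

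Section 11, Hypothesis 1a: the assessors' diagnosis is also to confirm the primary SCIPI metric.

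**The concern.** When a predictor is one of the inputs to the outcome, the two can be associated even if the predictor carries no information about the condition. If the assessors give QST any weight at 12 months, and a person's QST at 12 months resembles that person's QST at baseline, then baseline QST will tend to predict the diagnosis whether or not early sensory function predicts pain. Aim 2 is one of the study's two stated primary objectives, and the background presents prospective QST prediction as a main advance, so a positive QST-by-diagnosis result would draw attention.

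The confirmation of SCIPI is weakened by the same route. Section 9 allows that TENS may alter sensory function. A change in thresholds alone could then move some diagnoses without any change in reported pain. The documents give no basis for putting a number on this.

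**Working it through.** **1. The chain in the text**

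| Link | Where | Present? |
|---|---|---|
| QST feeds the diagnosis | Section 9, part ii | Yes, by name and cross-reference |
| Diagnosis is an Aim 2 outcome | Section 9, part ii; section 11, sub-analyses | Yes |
| QST is an Aim 2 predictor | Section 9, part iv; section 11, Hypothesis 2c | Yes |
| QST withheld from assessors, or barred as predictor of their diagnosis | Nowhere | No |
| Assessors blinded | Section 9, randomization and blinding | To allocation only |

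The plan does not say which session's QST the assessors see at 12 months. If only the 12-month results, the overlap with baseline QST is indirect, through the within-person correlation. If baseline results too, it is direct.

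**2. The plan's own Aim 2 figure**

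Section 11 states that 82 subjects give 80% power for f² = 0.10 at two-sided 0.05. With noncentrality 0.10 × 82 = 8.2 on 1 and 80 degrees of freedom, power is 0.808. Fisher's z with correlation √(0.10/1.10) = 0.302 gives 0.790. The figure reproduces. It is used here only for the sample size and test level.

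**3. Illustration of the bias**

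Inputs:
- n = 82, two-sided 0.05 (section 11).
- Share diagnosed neuropathic p = 0.45, the midpoint of the 60% and 30% in section 11 (assumption).
- Baseline-to-12-month QST correlation r. Table 1 gives an ICC of 0.50 for both cold and hot pain thresholds in SCI, with lower limit 0.28 and upper limits 0.67 and 0.66. Using an ICC as this correlation is an assumption.
- v, the share of variance in the assessors' judgement explained by 12-month QST. The documents give none; 10% is assumed, with 5% and 20% as the range.
- No true link between baseline QST and pain. QST moves the judgement in one direction only (assumption).

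Formulas:
- Correlation of baseline QST with the underlying judgement: r√v.
- Splitting the judgement into yes/no multiplies this by φ(z_p)/√(p(1−p)) = 0.3958/0.4975 = 0.796. Call the result c.
- m = atanh(c) × √(82 − 3). The false-positive rate is Φ(m − 1.96) + Φ(−m − 1.96).

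For v = 0.10:
- r = 0.50: r√v = 0.158, c = 0.126, m = 1.124, rate = Φ(−0.836) + Φ(−3.084) = 0.202 + 0.001 = 0.203.
- r = 0.28: r√v = 0.0885, c = 0.0704, m = 0.627, rate = Φ(−1.333) + Φ(−2.587) = 0.091 + 0.005 = 0.096.

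| r | v = 5% | v = 10% | v = 20% |
|---|---|---|---|
| 0.28 | 7% | 10% | 14% |
| 0.50 | 12% | 20% | 36% |
| 0.67 | 19% | 33% | 58% |
| 0.90 | 30% | 54% | 84% |

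Simulation agrees: at v = 10% it gives 20.4% for r = 0.5 and 52.9% for r = 0.9. With zero weight the rate is the nominal 5%. Taking p = 0.60, the projected sham rate, leaves the r = 0.50 value at 20%.

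**4. Two variants, by simulation**

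- Only subjects with a pain can be classified. In the survey in section 3, 41 of 50 (82%) had a persistent pain. With that limit and r = 0.50, the rates at v = 5%, 10% and 20% are about 10%, 15% and 25%.
- Deviation in either direction counts equally toward the diagnosis. The rate is then 5% to 6% at every setting tried.

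**The case against.** The strongest reply concerns reach. A reader might infer that Hypothesis 2c itself can come out positive by construction. The documents do not support that. Section 11 first tests the predictors against presence and severity of neuropathic pain, and only then adds diagnostic category as separate sub-analyses. SCIPI ≥ 2 is called the primary metric for neuropathic pain, and severity is measured by NPSI or NRS; all are self-report and contain no QST. This stands, with one reservation: the SCIPI definition is written under Hypothesis 1a, and section 11 never names the presence outcome for Hypothesis 2c. That is an ambiguity, not evidence that the expert diagnosis is used.

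A reader might also take the 54% and 84% entries as the expected error. They do not fit Hypothesis 2c, whose predictors are pain thresholds and suprathreshold ratings. Table 1 puts pain-threshold reliability at 0.50, with upper limits of 0.67 and 0.66, and gives nothing for suprathreshold ratings. The r = 0.90 row applies to the vibration, cool and warm detection thresholds (ICCs 0.90 to 0.95) covered by the wider Aim 2 wording in section 9. No retest interval is given, and stability through the first year after injury may be lower.

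Direction matters as well. The background defines neuropathic pain by raised thresholds and/or allodynia and hyperalgesia. If assessors treat both as support, a linear association largely cancels. Practice may lie between the one-directional and symmetric cases.

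Finally, sensory signs belong to the protocol's definition of neuropathic pain, so using them in diagnosis is reasonable. That justifies the QST-informed diagnosis for clinical description. It does not make that diagnosis a sound outcome for testing QST as its predictor.

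**Conclusion.** The circularity is in the text and applies to two places: the Aim 2 sub-analyses that set QST against the assessors' diagnostic categories, and the use of that diagnosis as a confirmation of SCIPI. It does not touch the primary SCIPI comparison or the NPSI/NRS severity analyses. It reaches the main test of Hypothesis 2c only if the expert diagnosis is chosen as the presence outcome.

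Confidence in the structure is high; the size is unknown. For pain thresholds, a false-positive rate of about 10% to 20% against a nominal 5% is a fair illustration. It rests on an assumed 10% weight in one direction, the Table 1 reliability (0.50, lower limit 0.28) standing in for the correlation over the study interval, and QST able to influence the diagnosis of all 82 subjects. Limiting that influence to the 82% with pain brings the upper figure to about 15%, and a symmetric diagnostic rule brings it near 5%. Stable detection thresholds, or assessors who also see baseline QST, would push it up. The point should be addressed, but its scope is secondary.

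**What to change.** In section 11, name the Hypothesis 2c outcomes: SCIPI ≥ 2 for a pain at or below the level of injury for presence, and NPSI/NRS for severity. Then take one of two routes for the expert diagnosis.

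1. State that QST will not be used as a predictor wherever the QST-informed diagnosis is the outcome. This costs only text, but gives up the QST-by-diagnosis sub-analyses and leaves the confirmation of SCIPI as it is.
2. Have the same assessors first record and lock a classification with QST withheld, and use it for the QST-by-diagnosis sub-analyses and for the confirmation of SCIPI. The QST-informed diagnosis follows and is reported descriptively. This needs a change of order on the form and no new visits. Diagnoses already made can be repeated from the recorded items with QST withheld.

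The price of the second route is that the locked diagnosis omits sensory signs that are part of the protocol's own definition of neuropathic pain, so it is less complete for those analyses. The report should say so.
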